6.1. EFFICACY, VIROLOGIC AND PK MEASURES

Clinical Efficacy (clinical event scale of disease severity)

- 1 Death
- 2 Requiring mechanical ventilation and/or in ICU
- 3 Non-ICU hospitalization, requiring supplemental oxygen;
- 4 Non-ICU hospitalization, not requiring supplemental oxygen;
- 5 Not hospitalized, but with clinical and laboratory evidence¹⁰ of COVID-19 infection

Virologic measures

1. Rates and duration of SARS-CoV-2 molecular testing positivity at days 1, 7, 14, and 28
2. virological studies of SARS-CoV-2 RNA at days -1 to 0, 1, 7, 14, and 28

Pharmacokinetic (PK) measures: Anti-SARS-CoV-2 titers at days -1 to 0, 1, 7, 14 and 90.

Using samples from 20 donors, we will measure the viral growth inhibition titers of SARS-CoV-2 neutralizing antibodies compared to the current FDA benchmark neutralizing titer of 1:320. However, the ability to detect neutralizing antibodies for SARS-CoV-2 through true viral neutralization in culture is time consuming. Other approaches include in-house ELISA tests for the receptor binding subdomain on the external spike glycoprotein trimer, which correlate with viral culture neutralization in previous coronavirus work. Finally, there are an increasing number of non-FDA validated, commercial ELISA tests with the entire spike

¹⁰ Positive molecular test for SARS-CoV-2

glycoprotein trimer or nucleocapsid as capture proteins. The viral specificity of these commercial ELISA assays for antibodies to the more frequent common cold beta coronavirus like OC43 or the rare SARS-CoV-1 as well as sensitivity for SARS-CoV-2 antibodies is evolving in the ongoing pandemic. Therefore, we will compare the SARS-CoV-2 donor plasma neutralizing titer levels to the whole protein commercial ELISAs being adopted by hospitals versus the receptor binding domain ELISAs. The goal will be to accurately determine the correlation of serum antibody titers measured by the two ELISA assays to virus neutralization titers determined with SARS-CoV-2 live virus.

7. RISKS AND BENEFITS

Potential Benefits of treatment

The potential benefits of antiviral treatment with anti-SARS CoV-2 plasma in patients at high risk for developing COVID-19 due to a close contact with another individual with COVID-19 are unknown. However, it is anticipated that treatment will decrease the risk of developing symptomatic disease and decrease the severity of illness should it develop.

Potential benefits of clinical monitoring and virologic testing

Subjects enrolled in the study will undergo close clinical and virologic monitoring that could facilitate earlier diagnosis of development of COVID-19 with associated benefit to the individual, their family and the community at large.

Potential risks

1. Risks of plasma: Fever, chills, rash, headache, serious allergic reactions, TRALI, TACO, transmission of infectious agents
2. Risks of phlebotomy: local discomfort, bruising, hematoma, bleeding, fainting,
3. Total blood draws will not exceed 500 mL
4. Risks of oropharyngeal and throat swab: local discomfort, vomiting

Alternatives

The alternative to participation in this study is routine care and monitoring following close contact with an individual with COVID-19

Safety measures

1. Safety Evaluations will assess for the safety of high titer anti-SARS-CoV-2 plasma and determine if it is higher, lower or the same as SARS-CoV-2 non-immune plasma
2. Clinical evaluations: In-person vital signs and symptom screen on days 0,1,7,14 and remote (phone call) symptom screens on days ,3 and 60
3. Laboratory evaluations

4. Safety laboratory tests (ABO typing, pregnancy testing, CBC and comprehensive metabolic panel) will be performed at the local CLIA-certified clinical laboratory on days -1 to 0, 1, 7 and 14

Event (AE)

Any untoward medical occurrence in a clinical investigation subject who has received a study intervention and that does not necessarily have to have a causal relationship with the study product. An AE can, therefore, be any unfavorable and unintended sign (including an abnormal laboratory finding, for example), symptom, or disease temporally associated with the use of the study product, whether or not considered related to the study product.

Serious Adverse Event (SAE)

An SAE is any adverse event that results in any of the following outcomes:

1. Death;
2. Life-threatening (immediate risk of death);
3. Inpatient hospitalization or prolongation of existing hospitalization;
4. Persistent or significant disability or incapacity;
5. Congenital anomaly/birth defect;
6. Important medical events that may not result in death, be life threatening, or require hospitalization may be considered a serious adverse event when, based upon appropriate medical judgment, they may jeopardize the subject and may require medical or surgical intervention to prevent one of the outcomes listed in this definition. Examples of such medical events include allergic bronchospasm requiring intensive treatment in an emergency room or at home, blood dyscrasias or convulsions that do not result in inpatient hospitalization, or the development of drug dependency or drug abuse.

Unexpected Adverse event: (UAE): An adverse reaction, the nature or severity of which is not consistent with the investigator's brochure.

Serious and Unexpected Suspected Adverse Reaction (SUSAR)

Investigators should report SUSARs to Johns Hopkins University within 5 calendar days of awareness. Johns Hopkins will submit the SUSARs to the FDA within 15 calendar days. Fatal or life-threatening SUSARs should be reported to Johns Hopkins as soon as possible and no later than 3 calendar days of awareness. Fatal or life-threatening SUSARs will be reported to the FDA within 7 calendar days.

Unanticipated Problem (UP)

Unanticipated Problem that is not an Adverse Event (e.g. breaches of confidentiality, accidental destruction of study records, or unaccounted-for study drug).

Protocol Deviation

Deviation from the IRB-approved study procedures. Designated major and minor:

1. Major Protocol Deviation: Protocol deviation that compromises trial integrity and/or the safety, welfare or rights of subjects or others
2. Minor Protocol Deviation: Other protocol deviation

Sites should follow their IRB guidelines for reporting.

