5.2.1. Analysis of AE data

Analysis of AE data will primarily be descriptive based on MedDRA coding of events. The proportion of subjects experiencing an SAE and the proportion experiencing a Grade 3 or higher. AE will be compared between randomized arms using Fisher’s Exact Test.

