## **Adverse events of study treatment:**

We hypothesize that participants randomized to convalescent plasma will not have any increased risk to standard transfusions. Preliminary data from the expanded access protocol for treatment of COVID-19 by convalescent plasma among those with severe disease, suggests that the treatment is safe with low number of adverse events [Joyner et al, J Clin Invest. 2020].

Adverse event data will be collected continuously throughout the trial and analyzed by treatment group at each interim analysis. We will also compare the rates of all serious adverse events (as

specified by the Health and Human Services definition) using cumulative incidence. The primary safety endpoints are i) the cumulative incidence of treatment-related serious adverse events categorized separately as either severe infusion reactions or Acute Respiratory Distress Syndrome (ARDS) during the study period and ii) cumulative incidence of treatment-related grade 3 and 4 adverse events during the study period.

Data collection for adverse events will be done via a combination of specific questions for anticipated effects and spontaneous participant report. We will present overall number of AEs and SAEs by treatment group and where differences exist, we will present those by organ system. As these are descriptive safety analyses no correction for multiplicity will be undertaken.

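### The plan poses a question of equal safety but specifies no interval for the between-arm safety difference, and a non-significant Fisher's exact test cannot answer that question

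*Protocol*

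**What the plan says.** Safety is listed as a primary objective (Protocol sections 1 and 4.1.2). Its primary endpoints are severe infusion reactions, ARDS, and grade 3 and 4 adverse events (Protocol 5.3).

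Two statements set the question:
- Protocol section 7, under safety measures, says the evaluations will "determine if it is higher, lower or the same as SARS-CoV-2 non-immune plasma".
- The SAP section on adverse events of study treatment states: "We hypothesize that participants randomized to convalescent plasma will not have any increased risk to standard transfusions".

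The methods offered are these:
- Protocol 5.2.1 begins "Analysis of AE data will primarily be descriptive based on MedDRA coding of events". It then takes the proportion with an SAE and the proportion with a grade 3 or higher AE, and says of the comparison: "AE will be compared between randomized arms using" Fisher's exact test. It gives no alpha or sidedness for safety.
- The SAP does not name Fisher's test. It compares all SAEs by cumulative incidence, presents AE and SAE numbers by arm, and adds: "As these are descriptive safety analyses no correction for multiplicity will be undertaken". It limits the primary safety endpoints to treatment-related events, a limit that Protocol 5.3 does not contain.

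No margin or between-arm interval is given for any safety endpoint. The 95% intervals in Protocol 5.2 belong to the primary efficacy analysis. Those in Protocol 8.3 (Tables 2 and 4) are single-arm limits, based on 15 and 4 expected symptomatic participants out of 75 per arm.

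**The concern.** Both statements are comparative, and both allow a conclusion that the arms do not differ. Fisher's test takes equality as its null hypothesis, so failing to reject it is not evidence for equality. If events are few, the test may well be non-significant whether or not HCIP carries excess risk. The plan specifies nothing that shows how large an excess the data leave open.

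At stake is the safety sentence in the final report. Without an interval, a reader cannot tell a trial that excluded a meaningful excess from one that was too small to see it.

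**Working it through.** **Inputs.** 500 participants randomised 1:1, so 250 per arm (Protocol 5.1). Fisher's exact test (Protocol 5.2.1). Two-sided 0.05 is assumed because no safety alpha is stated; one-sided 0.05 is also shown. Control SAE rates are assumed over a range because the documents give none.

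**The plan's own figures.** The documents state no power or precision for safety. The one stated sample size is for efficacy: 13% vs 6.5%, one-sided 0.05, 80% power, 488 in total. On an exponential model the hazard ratio is ln(0.935)/ln(0.87) = 0.4826. Required events are 4 × (1.645 + 0.842)² / (ln 0.4826)² ≈ 46.6, rounded up to 47. Dividing by the mean event probability of 0.0975 gives about 482, close to 488. The size was therefore set by efficacy. The death probabilities in Protocol 8.3, Table 1, also reproduce: 1 − (1 − 0.014)^15 = 0.191.

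**Miss rate of Fisher's test.** For each pair of true risks, the binomial probabilities (n = 250 per arm) are summed over all tables with p ≤ 0.05 and more events on HCIP. The miss rate is 1 minus that sum.

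| Control vs HCIP (assumed) | Missed, two-sided | Missed, one-sided |
|---|---|---|
| 1% vs 2% | 93% | 88% |
| 2% vs 4% | 82% | 73% |
| 4% vs 8% | 59% | 47% |
| 5% vs 10% | 49% | 37% |
| 1% vs 3% | 76% | 65% |
| 2% vs 6% | 44% | 32% |
| 3% vs 9% | 22% | 14% |
| 5% vs 15% | 4% | 2% |

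The two-sided miss rate passes 50% at a control rate of about 4.9% for a doubling and about 1.8% for a tripling. One-sided, these points are about 3.7% and 1.4%.

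**Example, 5 vs 0 events.** Given five events in total, the chance that all fall in one named arm is (250·249·248·247·246)/(500·499·498·497·496) = 0.0306, so the two-sided p is 2 × 0.0306 = 0.061. The Wilson limits are 0.857% to 4.596% for 5/250 and 0% to 1.513% for 0/250. Newcombe's interval for the difference of 2.0 points is then:
- lower: 2.0 − √[(2.0 − 0.857)² + 1.513²] = 2.0 − 1.896 = +0.1
- upper: 2.0 + √[(4.596 − 2.0)² + 0²] = +4.6

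Against 0 control events, Fisher's test needs 6 on HCIP to reach p ≤ 0.05 (6 vs 0 gives p = 0.030).

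**Other splits.** 8 vs 3 gives p = 0.22 and an interval of −0.8 to +5.1 points. 5 vs 5 gives p = 1 and an interval of −2.8 to +2.8 points.

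**The case against.** The strongest reply is that both documents call the adverse-event analysis descriptive. The SAP does not name Fisher's test, and it tabulates events by arm, so a 5 vs 0 split would be visible. No rule turns p > 0.05 into a statement of equal safety, and the line in Protocol section 7 is one item in a general list. Protocol 8.3 adds event-triggered halting and DSMB review of deaths and ARDS.

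Much of this stands, and it rules out several stronger readings that a reader might infer:
- **That the test misses a doubling or tripling of serious events in most trials.** The documents give no SAE rate, and several plausible pairs in the table are missed in fewer than half of trials. More frequent events, which grade 3 or higher AEs may be, would be better powered.
- **That the safety conclusion rests on Fisher's test alone, or that the plan would report a non-significant result as equal safety.** The documents say neither. Fisher's test is only the one between-arm test they name.
- **That the miss rate breaches a 20% limit.** The only such figure is the Type II error for efficacy in Protocol 5.1.
- **That ARDS would almost always be missed.** Protocol 5.2.1 does not assign Fisher's test to ARDS. Multiplying 13% symptomatic by the cited 3.4% gives 0.44%, a product the plan never forms. Its own ARDS section assumes 20% symptomatic and a 40% worst case. Even 13% × 40% = 5.2% would leave a tripling missed only 3% of the time.

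The descriptive label does not remove the gap. A descriptive analysis should give an estimate with its uncertainty, and none is specified. The halting rules and DSMB review protect participants during the trial, but they do not bound the arm difference in the final report.

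**Conclusion.** The concern holds in a limited form. The plan sets out to judge whether safety is the same and hypothesises no increased risk, but specifies no between-arm interval from which either could be judged. That gap does not depend on the event rate.

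Its practical size does. At 250 per arm and two-sided 0.05, a doubling is missed in most trials only below a control rate of about 5%, and a tripling only below about 1.8%. These figures rest on assumed rates, an assumed alpha and full enrolment; slightly smaller analysed arms would raise the miss rates a little.

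The 5 vs 0 example does not prove harm. Newcombe's interval is less conservative than Fisher's test, and an exact interval might not exclude zero. It does show what the p-value alone conceals: an excess of up to 4.6 points remains open.

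**What to change.** In Protocol 5.2.1 and the SAP adverse-event section:
1. Report the risk difference (HCIP minus control) with a two-sided 95% interval suited to rare events, such as Newcombe or exact, for each primary safety endpoint and for any SAE. Name one method in advance and keep Fisher's p as supportive.
2. Replace "determine if it is higher, lower or the same as SARS-CoV-2 non-immune plasma" in Protocol section 7 and "will not have any increased risk to standard transfusions" in the SAP with estimation wording. State that a non-significant p-value will not be reported as equal safety.
3. Reconcile the two documents: Fisher's test on any SAE and grade 3 or higher AEs in Protocol 5.2.1, against cumulative incidence and treatment-related primary endpoints in the SAP.

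A margin fixed before unmasking is needed only if the sponsor wants to claim similar safety; otherwise it is optional.

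The cost is wording and an extra column in the safety tables, with no added participants or data. The downside is a less favourable safety statement: even 5 vs 5 events leaves an excess of up to about 2.8 points not excluded.

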7.1. Reporting Interval

All AEs and SAEs will be documented from the first administration of study product All AEs and SAEs will be followed until resolution even if this extends beyond the study-reporting period. Resolution of an adverse event is defined as the return to pre-treatment status or stabilization of the condition with the expectation that it will remain chronic.

Reporting should also occur at any time after completion of the study, if the investigator becomes aware of a SAE that is suspected to be related to study product

Investigator's Assessment of Adverse Events

The determination of seriousness, severity, and causality will be made by an on-site investigator who is qualified (licensed) to diagnose adverse event information, provide a medical evaluation of adverse events, and classify adverse events based upon medical judgment. This includes but is not limited to physicians, physician assistants, and nurse practitioners.

Laboratory abnormalities will be reported as AEs if they are considered clinically significant by the investigator.

Assessment of Seriousness

- I. Event seriousness will be determined according to the protocol definition of an SAE
- II. Assessment of Severity

Event severity will be assigned according to the MedDRA parameters in the EDC, which correspond to the following definitions:

- 1 = Mild: Transient or mild discomfort (<48 hours); no medical intervention/therapy required.)
- 2 = Moderate: Mild to moderate limitation in activity-some assistance may be needed; no or minimal medical intervention/therapy required)
- 3 = Severe: Marked limitation in activity, some assistance usually required; medical intervention/therapy required, hospitalizations possible
- 4 = Life-threatening: Extreme limitation in activity, some assistance usually required; medical intervention/therapy required, hospitalization or hospice care probable
- 5= Death

Assessment of Association

The association assessment categories that will be used for this study are:

- Associated – The event is temporally related to the administration of the study product and no other etiology explains the event.
- Not Associated – The event is temporally independent of the study product and/or the event appears to be explained by another etiology.

The investigator must provide an assessment of association or relationship of AEs to the study product based on:

- Temporal relationship of the event to the administration of study product;
- Whether an alternative etiology has been identified;
- Biological plausibility;
- Existing therapy and/or concomitant medications.

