Our analysis will be a time to event analysis examining the effect of anti-SARS-CoV-2 plasma. We will estimate the survival function for each treatment arm in order to estimate the risk difference over time as well as the restricted mean survival time which is the area under the survival function and provides the expected mean time to hospitalization or death up to time t^{22} . Our approach will be to estimate the cumulative incidence using the doubly robust estimator based upon targeted minimum loss based estimator as described by Diaz et al [Díaz, I., Colantuoni, E., Hanley, D.F. *et al.* Improved precision in the analysis of randomized trials with survival outcomes, without assuming proportional hazards. *Lifetime Data Anal* **25**, 439–468 (2019)]. By adjusting for baseline covariates that are related to the outcome, we increase precision. The TMLE based approach was shown to increase precision by around 10% to 20% over an inverse probability weighted or augmented inverse probability weighted estimator. As stated above, we will use a hybrid approach of adjusting for pre-specified variables (age) and an algorithmic approach to identify additional variables related to the outcome. Specifically, a random survival forest will be used to identify variables that are related to the outcome in order to increase precision. We will use a random survival forest blinded to the treatment arm allocation and *not* including an indicator variable for treatment. The following pre-randomization variables will be considered: clinical site, race, ethnicity, sex, category of exposure, hematology factors and other laboratory markers (i.e., CBC and metabolic panels), body mass index, ABO blood group, targeted physical exam, and prior comorbidities that have specifically been associated with worse COVID-19 outcomes including: asthma, chronic kidney disease, chronic lung disease (COPD, idiopathic pulmonary fibrosis, cystic fibrosis), diabetes, hemoglobin disorders (thalassemia, sickle cell disease), immunocompromised (cancer, HIV, organ transplantation, prolonged use of corticosteroids), chronic liver disease,

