6. STUDY PROCEDURES

Day -1 to 0

In-person visit

- A. Screening (must be completed before randomization)
- B. Informed consent (may be obtained prior to Day-1 and before performing study related activities)
- C. Baseline Evaluation (at screening)
 1. Demographics (Age, sex ethnicity, race, number of people in household)
 2. Medical history (timing of exposure to COVID-19 source patient, acute and chronic medical condition, medications, allergies. Any medical condition arising after consent should be recorded as AE)
 3. COVID-19 symptom screen (fevers, cough, shortness of breath)
 4. Vital signs
 6. COVID-19 molecular testing prior to infusion, from nasopharyngeal, throat samples (may be omitted if test already performed on same day as part of usual care)
 7. Draw and result ABO and Rh if no documented ABO typing within the past year.
 8. CBC, comprehensive metabolic panel
 9. Stored samples for future studies

10. Urine or serum pregnancy test for females of childbearing potential. Results from laboratory tests obtained up to 7 days before randomization may be used for the pregnancy test.
11. Determination of eligibility as per inclusion/exclusion criteria
12. Confirmation of emergency contact information in EMR.

To the extent possible and with goal of minimizing exposure of health care workers and study team members to risk, there will be a pre-visit explanation and consent done using a video platform at sites that permit video platform use.

Day 0

In-person visit

1. Randomization of eligible subject in IWRS
2. Study Plasma Administration: A single unit of plasma will be transfused. Time at start and end of infusion will be recorded and Vital signs will be measured immediately prior to infusion, 10-20 minutes after start of infusion, at completion of infusion and 30-60 minutes after the end of the infusion.
3. COVID-19 symptom screen (fevers, cough, shortness of breath). Done by telephone before they come in for transfusion.
4. Assessment of clinical status (composite outcome of disease severity)
5. New medical conditions, concomitant medication, AE evaluation
6. Physical examination

Day 1, (+/-) 1 day

In-person visit

1. Vital signs
2. COVID-19 symptom screen (fevers, cough, shortness of breath)
3. Assessment of clinical status (clinical event scale of disease severity)
4. New medical conditions, AE evaluation
5. CBC, comprehensive metabolic panel
6. COVID-19 molecular testing from nasopharyngeal, throat samples

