8.3. Halting Criteria for the Study

The study enrollment and dosing will be stopped and an ad hoc review will be performed if any of the specific following events occur or, if in the judgment of the study physician, subject safety is at risk of being compromised:

- I. Unexpected death of a dosed subject in relation to infusion
- II. Occurrence of a life-threatening allergic/hypersensitivity reaction (anaphylaxis), manifested by bronchospasm with or without urticaria or angioedema requiring hemodynamic support with pressor medications or mechanical ventilation.
- III. One subject with an unexpected SAE associated with study product.
- IV. Two subjects with a Grade 3 or higher toxicity for the same parameter associated with study product.
- V. An overall pattern of symptomatic, clinical, or laboratory events that the medical monitor, ISM, or SMC consider associated with study product and that may appear minor in terms of individual events but that collectively may represent a serious potential concern for safety.
- VI. Any other event(s) which is considered to be a serious adverse event in the good clinical judgment of the responsible physician. This will be appropriately documented.

Interim Analyses for efficacy: There will be two formal review of interim results. The first will occur after 15 infections which is expected to occur near 150 participants reaching day 28 and the second after 50% of the total recruitment (n=500) has been achieved and these individuals followed to at least day 28. Interim analyses will only be adjusted for age. Stopping guidelines will be based on O’Brien-Flemming boundary. The interim analysis Z-value boundary of 3.03 (nominal p-value of 0.0011, spent alpha 0.0011), 2.38 (0.0087, 0.008), and 1.68 (0.464, 0.408) for a one-sided test with Type 1 of 0.05.

Special considerations for death:

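### Post-infusion CBC and metabolic panel values reach the visible safety analysis only as investigator-reported AEs, graded on a scale with no laboratory limits; grade them numerically and tabulate them by arm

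*Protocol*

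**What the plan says.** **Collection.** Protocol section 7 (Safety measures) names the tests and gives their schedule, which is screening plus three days after infusion: "Safety laboratory tests (ABO typing, pregnancy testing, CBC and comprehensive metabolic panel) will be performed at the local CLIA-certified clinical laboratory on days". The visit lists in section 6 agree, with "CBC, comprehensive metabolic panel" at screening and on days 1, 7 and 14.

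**Reporting.** Section 7.1 sets the entry rule: "Laboratory abnormalities will be reported as AEs if they are considered clinically significant by the investigator". The on-site investigator decides seriousness, severity and causality by medical judgment.

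**Grading.** Section 7.1 states: "Event severity will be assigned according to the MedDRA parameters in the EDC, which correspond to the following definitions". Five levels follow. Grade 3 reads "3 = Severe: Marked limitation in activity, some assistance usually required; medical intervention/therapy required, hospitalizations possible". Grade 4 is built the same way, with extreme limitation. Grade 1 involves no therapy, and grade 2 none or minimal. No CBC or metabolic panel limit is printed and no laboratory toxicity table is named.

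**Use of the grades.** Grade 3 and 4 AEs are a primary safety endpoint (Protocol 5.3; SAP, Adverse events of study treatment). Protocol 5.2.1 compares two proportions by Fisher's exact test: "The proportion of subjects experiencing an SAE and the proportion experiencing a Grade 3 or higher" AE. Halting criterion IV in section 8.3 is "Two subjects with a Grade 3 or higher toxicity for the same parameter associated with study product".

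**Use of the laboratory values.** The only visible analytic use is as pre-randomization candidate covariates in Protocol 5.2, "hematology factors and other laboratory markers (i.e., CBC and metabolic panels), body mass index, ABO blood group", and in the matching list in the SAP (Statistical Principles). The SAP safety section counts AEs and SAEs by arm. It contains no laboratory summary or shift table.

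**The concern.** Two judgments stand between a laboratory change and any comparison by arm: whether it is clinically significant, and which grade it receives. The printed scale guides the second poorly, because it describes what the subject experiences and what therapy is needed, not how far the value has moved. A sizeable change in a subject who feels well and needs no treatment has no home in grade 3 or 4.

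Two things are at stake. Criterion IV refers to a parameter but has no parameter limits behind it, so it may not count such changes. And the values themselves, although collected in everyone on a fixed schedule, may never be set side by side by arm. The safety section of the protocol says the evaluations should show whether convalescent plasma is more, less or equally safe than control plasma. For silent laboratory changes, no visible analysis does that.

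**Working it through.** **Textual check.** Take an abnormality that is asymptomatic and needs no treatment.

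1. Is it an AE? Only if the investigator calls it clinically significant (7.1).
2. Which grade? Grades 3 and 4 combine activity limitation with required therapy. Neither element is present, so the wording of grades 1 and 2 fits.
3. Does criterion IV count it? Not at grade 1 or 2.
4. Does any visible analysis use the value directly? No. Protocol 5.2.1 and the SAP safety section work from reported AEs, and the covariate lists use baseline values.

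The wording is therapy *required*, not therapy given. A value that needs treatment and has not yet had it can fit grade 3, and one judged life-threatening can be graded 4. The gap is confined to changes that neither limit activity nor require treatment.

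**Illustration 1: criterion IV, given k affected subjects.** The documents state no figure to reproduce and give no laboratory event rates, so every rate below is an assumption. Let k subjects share one product-associated abnormality, each graded 3 or higher with probability q.

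P(at least 2 graded) = 1 − (1−q)^k − kq(1−q)^(k−1)

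| k | q = 25% | q = 50% | q = 75% |
|---|---|---|---|
| 2 | 6% | 25% | 56% |
| 3 | 16% | 50% | 84% |
| 4 | 26% | 69% | 95% |

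Example, k = 3 and q = 0.5: 1 − 0.125 − 3 × 0.5 × 0.25 = 0.50.

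**Illustration 2: criterion IV over the active arm.** Inputs: 250 subjects (500 randomized 1:1, all infused) and true rate p. P = P(Bin(250, pq) ≥ 2).

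| p | q = 100% | q = 50% | q = 25% |
|---|---|---|---|
| 0.4% | 26% | 9% | 3% |
| 1% | 71% | 36% | 13% |
| 2% | 96% | 71% | 36% |

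These figures hold only for toxicity specific to convalescent plasma. For a reaction to plasma in general at 1% in both arms, the count runs over 500 subjects. P(Bin(500, 0.01q) ≥ 2) is then 96%, 71% and 36% for q = 100%, 50% and 25%.

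**Illustration 3: comparison by arm.** Two-sided Fisher's exact test at 0.05, 250 per arm, exact enumeration, rejections with active above control. In the pooled grade 3+ test, the arm rate is 1 − (1−b)(1 − laboratory rate × share graded), where b is an equal clinical background.

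| Laboratory rate, control v active | b | Power, all graded 3+ | Power, half graded 3+ |
|---|---|---|---|
| 2% v 6% | 0 | 56% | 24% |
| 2% v 6% | 5% | 27% | 10% |
| 1% v 4% | 0 | 48% | 16% |
| 2% v 8% | 0 | 86% | 48% |

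The pooled test is weak at a 5% background even with perfect grading. A separate laboratory table is not diluted by clinical events: its counts correspond to the b = 0, all-graded column.

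**The case against.** The strongest reply has five parts.

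*The operative grading source is unseen.* Grades come from parameters in the electronic data capture system, and the printed lines are only what those correspond to. Protocol section 8.1, the opening part of the SAP, the Data Safety Monitoring Plan and the DSMB charter were also not available. This stands: the absence is claimed for the visible text only.

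*A consequence-based scale is coherent.* Not calling a change severe when it limits nothing and needs no treatment is defensible. That stands for the clinical endpoint, which is why the clinical scale should stay. It does not explain why scheduled safety values should go unsummarized.

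*Other halting rules cover the case.* A reader might infer that the trial cannot halt for laboratory toxicity, or that criterion IV was written for laboratory signals and is now inoperative. The documents support neither. Criterion IV never mentions laboratory values. Criterion V does, reaches patterns of individually minor events, and needs no grade. Criteria III and VI need no grade either, and the SAE definition gives blood dyscrasias as an example. What remains is that each route needs someone to notice or report the change, and no visible table by arm would help them.

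*Numeric grades could stop a trial that must enroll within 96 hours of exposure.* Section 8.3 stops enrollment and dosing when a criterion is met. This stands, and it argues against tying a stop mechanically to a numeric grade.

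*The sizes rest on assumed rates, for safety analyses the SAP calls descriptive.* True. They show direction and sensitivity only.

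A reader might also suspect bias between arms. Site staff are masked and randomization is stratified by site (SAP, Randomization), so uneven grading between sites is unlikely to favor an arm.

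**Conclusion.** The point holds in a limited form. In the visible text, post-infusion CBC and metabolic panel values reach the safety analysis only through investigator-reported AEs. The scale then places a change that neither limits activity nor requires treatment in grade 1 or 2, whatever its size. Criterion IV is weakened for such changes, and the values are not compared by arm.

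The size cannot be fixed from the documents. Under the assumptions shown, the chance that criterion IV is met at a 1% rate specific to convalescent plasma falls from 71% to 36% or 13% when half or a quarter of the events are graded 3 or higher. If subjects in both arms are affected at 1%, the fall is from 96% to 71% or 36%. All of this assumes that association with product is accepted.

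The primary efficacy analysis is not affected. This is a worthwhile, inexpensive improvement to safety reporting, not a fault that undermines the trial. If the data capture system already holds a numeric laboratory table, the grading part reduces to citing it; the display by arm would still be needed.

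**What to change.** 1. In Protocol 7.1, name one published numeric laboratory toxicity table, or cite the one in the data capture system if it has one.
2. Apply it by program to the day 1, 7 and 14 CBC and metabolic panel values, counting grades that are new or worse than at screening.
3. In the SAP, add a separate descriptive table of laboratory grade 3 or higher by arm, supplied to the DSMB at each interim.
4. State in Protocol 8.3 that a flagged value prompts the investigator to assess clinical significance and association, and that the result informs criteria IV and V. A flag alone should not stop enrollment.
5. Leave the clinical grade 3 and 4 endpoint and the planned Fisher tests as they are.

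The cost is a derivation program, with no new tests or visits, and some flagged values of little clinical importance. If 2% of subjects had one (an assumption), that is 0.02 × 500 = 10 assessments over the trial. The pooled grade 3+ test gains no power from this; the gain is that silent changes become visible by arm.
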